7.4.1.3 Assessment of Health

Days 10 to 14

The patient will self-assess his or her health on a scale of 0 (Worst possible health) to 10 (Normal health [for someone your age and condition]) and record it in the patient eDiary, predose on Day 1 and then once daily (evening) until Day 14. Table 7-3 provides the time windows of assessment as a guide.

Time Windows of Assessment as a Guide: Assessment Table 7-3 of Health

Assessment Period	Time Period of a Day	Time Window as a Guide
Days 1 to 14	Evening	18:00 -

Assessment of health prior to influenza symptoms will be performed predose on Day 1 and recorded in either the eDiary or a paper diary (see Appendix 4).

CPI 7.4.1.4

TheCPI will be recorded in the patient eDiary. The details of the measurement are described in the Section 7.7.4.1.

7.4.2 Virology Test

Two nasopharyngeal/pharyngeal swabs (nasopharyngeal swabs are the preferred method of virology collection as they are the most accurate, but pharyngeal swabs will be acceptable if nasopharyngeal swabs cannot be performed) will be collected predose at Visit 1 (Day 1 at the same time as the RIDT), Visit 2 (Day 2), Visit 3 (Day 3), Optional Visit 1 (Day 4), Visit 4 (Day 5), Optional Visit 2 (Day 6), and Visit 5 (Day 9), as well as at Visit 6 (Day 15) and Visit 7 (Day 22) if the investigator determines that flu symptoms are persisting. Specimens will be handled according to Section 7.6.4.5.

The virology testing facility (see Section 10.1) will perform virus typing and subtyping, determination of virus titer and viral RNA load, according to procedures or a protocol specified in a separate document. Access to the virological endpoints will be limited. Specific details of who will have access to each endpoint will be specified in a separate document.

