9.10.2 Secondary Efficacy Endpoints

The secondary efficacy endpoints include the following variables.

1) Proportion of patients positive for virus titer and proportion of patients positive by RT-PCR at each time point

Defined as the percentage of patients whose virus titer is not < the lower limit of quantification among those assessed for virus titer, and the percentage of patients with detectable virus RNA among assessed by RT-PCR, respectively.

2) Change from baseline in virus titer and in the amount of virus (RT-PCR) at each time point

Defined as the change from baseline in virus titer and the change from baseline in the amount of virus RNA, respectively. Baseline is defined as the last value obtained before the initial dose.

3) AUC adjusted by baseline in virus titer and in the amount of virus RNA (RT-PCR)

Defined as AUC, where AUC is the area under the curve, of change from baseline in virus titer and AUC of change from baseline in the amount of virus RNA, respectively. AUC is calculated using the trapezoidal method.

4) Time to cessation of viral shedding by virus titer and by RT-PCR

Defined as the time between the initiation of the study treatment and first time when the virus titer is < the lower limit of quantification and the time between the initiation of the study treatment and first time when virus RNA by RT-PCR is < the lower limit of quantification, respectively.

5) Proportion of patients whose symptoms has been alleviated at each time point

Defined as the percentage of patients whose primary endpoints are improved after the initiation of the study treatment in the analysis population by each time point. 6) Time to alleviation of symptoms (cough, sore throat, headache, nasal congestion, feverishness or chills, muscle or joint pain, and fatigue)

Defined as the time between the initiation of the study treatment and the alleviation of influenza symptoms. The alleviation of influenza symptoms is defined as the time when all of 7 influenza symptoms have been assessed by the patient as 0 (None) or 1 (Mild) in the patient eDiary, for a duration of at least 21.5 hours (24 hours -10%).

7) Time to improvement in the 4 systemic symptoms (headache, feverishness or chills, muscle/joint pain, and fatigue)

Defined as the time between the initiation of the study treatment and the improvement in the 4 systemic symptoms. The assessment follows the criteria for the primary endpoint.

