9.10.3.2 Analyses of Secondary Endpoints

1) Proportion of patients positive for influenza virus titer and proportion of patients positive by RT-PCR at each time point

Only patients whose virus titer/RT-PCR predose at Visit 1 are \geq the lower limit of quantification will be included in the analyses. The summary table by each time

point will be made. The Mantel-Haenszel test at each time point will be used to compare the proportion of patients with positive virus titer/RT-PCR between S-033188 and oseltamivir/placebo with baseline symptom score ($\leq 14, \geq 15$), preexisting and worsened symptom (Yes, No), and region (Asia, North America/Europe, Southern Hemisphere) as stratification factors.

2) Change from baseline in virus titer and the amount of virus RNA (RT-PCR) at each time point

Only patients whose virus titer/RT-PCR predose at Visit 1 are \geq the lower limit of quantification will be included in the analyses. The van Elteren test will be used by each time point to compare the S-033188 with oseltamivir/placebo, where baseline symptom score ($\leq 14, \geq 15$), preexisting and worsened symptom (Yes, No), region (Asia, North America/Europe, Southern Hemisphere) will be included as stratification factors. Summary statistics will be calculated by time point and by treatment group.

3) AUC adjusted by baseline in virus titer and in the amount of virus RNA (RT-PCR)

Only patients whose virus titer/RT-PCR predose at Visit 1 are \geq the lower limit of quantification will be included in the analyses. The same statistical methods as 2) change from baseline in virus titer and the amount of virus RNA (RT-PCR) at each time point will be used. Summary statistics will be calculated by treatment group.

4) Time to cessation of viral shedding by virus titer and by RT-PCR

Only patients whose virus titer/RT-PCR predose at Visit 1 are \geq the lower limit of quantification will be included in the analyses. The same analyses as the primary endpoint will be performed.

5) Proportion of patients whose symptoms has been alleviated at each time point

The same analyses as 1) proportion of patients positive for influenza virus titer and proportion of patients positive by RT-PCR will be used.

6) Time to alleviation of symptoms

The same analyses as the primary endpoint will be performed.

 Time to improvement in the 4 systemic symptoms (headache, feverishness or chills, muscle/joint pain, and fatigue)

The same analyses as the primary endpoint will be performed.

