c The patient will measure or assess and record in the patient diary, body temperature 4 times daily (morning, noon, evening, and bedtime) from Days 1 to 3 and twice daily (morning and evening) from Days 4 to 14; assessment of health once daily (evening) from Days 1 to 14; the severity of influenza symptoms twice daily (morning and evening) from Days 1 to 9 and once daily (evening) from Days 10 to 14; and the CPI twice daily (morning and evening) from Days 1 to 9 and once daily (evening) from Days 2 or ET.

d Predose; if the study treatment is initiated at 18:00 or later on Day 1, the patient will not need to perform the Day 1 evening assessments.

e Including measurement of body weight.

f Height and body mass index will be measured at the predose examinations only.

g Urine pregnancy test will be performed only for females who are not diagnosed as postmenopausal.

h Predose.

i To be collected if the investigator determines that flu symptoms are persisting.

j If the investigator determines that flu symptoms are persisting at ET.

k Blood samples will be collected for the measurement of plasma drug concentrations once each at Visits 2 (Day 2) and 4 (Day 5). If circumstances permit, samples also will be collected within the period from 0.5 to 4 hours after the initial dose at Visit 1 (Day 1), at Visit 3 (Day 3), and at Visit 6 (Day 15).

Quality-of-Life Questionnaire Appendix 2

CPI

Study center name	
Patient identification code	
Visit	
Date	

Under each heading, please tick the ONE box that best describes your health TODAY.

CPI

CPI

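### Day 15 and Day 22 swabs are taken only from patients with persisting symptoms, so the between-arm virology tests at those two time points are not randomized comparisons

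*Protocol*

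**What the plan says.** Section 7.4.2 lists swabs predose and at Days 2, 3, 4, 5, 6 and 9 with no symptom condition (Days 4 and 6 are optional visits). It then adds two more, at Visit 6 (Day 15) and Visit 7 (Day 22), to be taken only "if the investigator determines that flu symptoms are persisting". The schedule in Appendix 1 repeats the condition in a footnote: "To be collected if the investigator determines that flu symptoms are persisting".

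Section 9.10.2, item 1, defines titer positivity as the percentage of patients "whose virus titer is not < the lower limit of quantification among those assessed for virus titer". The RT-PCR version is worded in the same way.

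Section 9.10.3.2 sets the tests. For positivity: "The Mantel-Haenszel test at each time point will be used to compare the proportion of patients with positive virus titer/RT-PCR". For change from baseline: "The van Elteren test will be used by each time point to compare the S-033188 with oseltamivir/placebo". The only restriction on who enters is a predose value at or above the limit of quantification. No time point is exempted.

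Time to cessation of shedding (item 4) is analysed like the primary endpoint. The AUC (item 3) is trapezoidal, and the protocol gives it no end time. Section 9.4 says that missing data are not replaced for the primary analyses. It has no rule for swabs that are absent by design.

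**The concern.** Whether a patient still has symptoms at Day 15 is known only after randomization. It is also close to what the primary endpoint measures and what S-033188 is meant to shorten. If only symptomatic patients are swabbed, the denominator at Days 15 and 22 is itself a result of treatment. The more effective arm contributes fewer patients, and probably a different kind: those who stayed ill despite treatment. A test between such subsets does not estimate the effect of assignment. It may show a difference where none exists, or hide one that does.

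The same rule reaches two other endpoints. A patient still positive at Day 9 has a later swab, and so a chance of an observed cessation time, only if symptoms persist. An AUC that used every available swab would cover a longer span in symptomatic patients than in recovered ones. Section 7.9.2 presents viral shedding as analogous to infectivity, so a misleading late result could be over-read.

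**Working it through.** **Inputs.** From Protocol Section 9.2: exponential times; median time to improvement 150 h (placebo) and 114 h (S-033188); 395 infected patients per arm; 336 h of follow-up; two-sided 5%; generalized Wilcoxon test; 55% RT-PCR positive. From Table 9-1: 126 h for oseltamivir. Day 15 is taken as 336 h and Day 22 as 504 h after first dose.

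**Step 1: reproduce the plan's figure.** With hazards λ = ln 2 / median, censoring at 336 h, numbers at risk y₁ and y₂, and weight W equal to the mean of the two survival curves:
- drift = ∫ W · y₁y₂/(y₁+y₂) · (λ₁−λ₂) dt
- variance = ∫ W² · y₁y₂/(y₁+y₂)² · (y₁λ₁+y₂λ₂) dt
- power = Φ(|drift|/√variance − 1.96)

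This gives 395 per arm for 90.0% power, as stated. Table 9-1 comes out at 22.2, 45.3, 71.5 and 90.2%, against 22.3, 45.3, 71.5 and 90.2%. Then 395/0.55 = 718.2, rounded up to 719, and 3 × 719 = 2157. The model below is therefore the protocol's own.

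**Step 2: who would be swabbed late.** Assumption: persisting symptoms means not having met the primary endpoint. The share remaining at time t is 2^(−t/median).

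| | S-033188 (114 h) | Oseltamivir (126 h) | Placebo (150 h) |
|---|---|---|---|
| Day 15, 336 h | 13.0%, about 51 of 395 | 15.7%, about 62 | 21.2%, about 84 |
| Day 22, 504 h | 4.7%, about 18 | 6.3%, about 25 | 9.7%, about 38 |

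For S-033188 and placebo together, about 83% have no Day 15 swab and about 93% no Day 22 swab. The swabbed share differs between these arms by a factor of 21.2/13.0 = 1.6 at Day 15 and 9.7/4.7 = 2.1 at Day 22. The visit windows move these counts. Visit 6 spans Days 12 to 18, or 264 to 408 h, which gives 79 versus 117 down to 33 versus 60 (S-033188 versus placebo).

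**Step 3: what selection can do at Day 15.** The protocol does not give the link between symptoms and virus, so three assumed cases are shown.

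*No link.* Positivity among those swabbed equals positivity overall, and there is no bias.

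*Equal number of carriers per arm, all symptomatic, no true difference* (placebo n = 84, S-033188 n = 51, unstratified Fisher test):

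| Carriers per arm | Placebo | S-033188 | p |
|---|---|---|---|
| 10 | 12% | 20% | 0.32 |
| 15 | 18% | 29% | 0.14 |
| 20 | 24% | 39% | 0.08 |
| 30 | 36% | 59% | 0.012 |

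The false difference runs against S-033188.

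*Shared severity, equal true positivity of 10%.* When a latent severity drives both symptoms and virus, simulated positivity among those swabbed is 11.9% (S-033188) versus 11.5% (placebo) with a weak link, and 25.1% versus 22.3% with a strong one. At these sample sizes that is about 6/51 versus 10/84 (p = 1.0) and 13/51 versus 19/84 (p = 0.83).

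**Step 4: a real benefit can vanish.** Suppose true Day 15 positivity is 5.0% on S-033188 and 8.16% on placebo, with every carrier symptomatic. Among those swabbed it becomes 0.050/0.1296 = 38.6% versus 0.0816/0.2117 = 38.5%.

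**The case against.** Several points on the other side carry weight.

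- **The counts are not protocol figures.** Section 7.4.2 leaves persistence to the investigator. Section 9.10.1 counts mild residual symptoms as alleviated and unworsened preexisting symptoms as maintained, so the two criteria differ. The virology analyses also require a quantifiable baseline value, so fewer than 395 per arm may enter. This stands: 84 versus 51 is an illustration.
- **A reader might infer that the plan will yield a significant false result against S-033188.** The documents do not support that. The value 0.012 needs 30 carriers per arm, all of them symptomatic, and neither figure is in the protocol. With 10 to 20 carriers, or under the shared-severity model, the difference is not significant. The planned test is also stratified, unlike the Fisher test used here.
- **A reader might infer that the AUC already ends at different times by symptom status.** The protocol gives no end time, and the SAP may set one. For cessation, the generalized Wilcoxon test weights early times, so events after Day 9 count least.
- **The persistence judgement is blinded.** It is, but this does not remove the selection, which works through the treatment effect and not through knowledge of assignment.
- **The SAP may limit the time points.** It may. But Section 9.1 says the SAP follows this section, and this section positively states a test at each time point.

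**Conclusion.** The point holds for the Day 15 and Day 22 tests of positivity and change. As written, they compare subsets chosen by a post-randomization outcome that treatment is expected to alter, and they cannot be read as randomized comparisons. That conclusion follows from the text and needs no assumption about numbers. The amount of bias does: it ranges from none to a false difference against S-033188, and a true benefit may also be masked.

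The reach is limited. These are secondary endpoints outside the hierarchy, which covers only the two comparisons of the primary endpoint. The primary result, the sample size and the tests through Day 9 are not affected by this rule. Severity is minor to moderate.

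**What to change.** In Section 9.10.3.2, limit the formal by-time-point tests of positivity and change to swabs through Visit 5 (Day 9). None of these carries a symptom condition, although the Day 4 and Day 6 swabs fall at optional visits, so their denominators should be shown by arm. Report Day 15 and Day 22 results descriptively, labelled as the symptomatic patients swabbed, with the number swabbed in each arm.

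For the same reason, state that the virology AUC ends at Day 9. Add an analysis of time to cessation that censors at the last swab through Visit 5; adding it beside the planned analysis keeps the later cessation times that were observed.

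The cost is protocol and SAP wording only, with no new swabs or visits. What is lost is the formal late-time tests, which have no clear interpretation as planned.

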7.4.3 Intrahousehold Infection Rate

For sites in Japan only, patients will be interviewed predose at Visit 1 (Day 1) about their household size, the number of household members infected this season before the patient is enrolled the study, and their diagnosis date (if the date is within 2 weeks) of influenza. From Day 1 to Day 15, the patient will be interviewed about the number of household members infected and their diagnosis date of influenza to evaluate the intrahousehold infection rate.

7.5 Pharmacokinetic Assessments

For the measurement of plasma S-033447 concentrations, blood samples will be collected at Visit 2 (Day 2) and Visit 4 (Day 5); if circumstances permit, samples will also be collected within the period from 0.5 to 4 hours after the initial dose at Visit 1 (Day 1), and at Visit 3 (Day 3) and Visit 6 (Day 15).

The actual time of each blood sample collection and the time of study drug ingestion will be recorded in the eCRF.

At each sample collection, blood will be drawn into a heparin sodium-containing tube, followed promptly by centrifugation to separate plasma. The resulting plasma will be stored at -20° C or below. Detailed procedures for the sample collection, handling, and shipping to the bioanalytical laboratory are specified in a separate document.

Plasma concentrations of S-033447 will be analyzed with a validated liquid chromatography-tandem mass spectrometry method.

7.6 Safety Assessments

7.6.1 Physical Examination

A full physical examination will be performed at Visit 1 (Day 1) and 7 (Day 22) according to the normal practice of the clinical study site by the investigator or subinvestigator in order to check for any AEs (see Section 7.6.5.1). In addition, symptom-focused physical examinations will be performed at Visit 2 (Day 2), Visit 3 (Day 3), Optional Visit 1 (Day 4), Visit 4 (Day 5), Optional Visit 2 (Day 6), Visit 5 (Day 9) and Visit 6 (Day 15). The patient will also be observed for any influenza-related complications (sinusitis, bronchitis, otitis media, and pneumonia) at all visits after Visit 1 (Day 1).

Height in centimeters and body weight in kilograms will be obtained and entered in the eCRF, along with BMI, at the predose examinations only.

7.6.2 Vital Sign Measurements

Blood pressure (systolic and diastolic), respiratory rate (breaths per minute), and pulse rate will be measured by the investigator or designee at Visit 1 (Day 1), Visit 2 (Day 2), Visit 3 (Day 3), Optional Visit 1 (Day 4), Visit 4 (Day 5), Optional Visit 2 (Day 6), Visit 5 (Day 9), Visit 6 (Day 15), and Visit 7 (Day 22). Blood pressure, pulse rate, and

respiratory rate will be measured after the patient has rested in a sitting position for at least 3 minutes.

The investigator or subinvestigator will consider whether any abnormal changes from baseline (predose at Visit 1, Day 1) are clinically significant (see Section 7.6.5.6). Results of blood pressure, pulse rate, and respiratory rate measurements will be entered in the eCRF.

7.6.3 Electrocardiography

12-lead ECG will be performed by the investigator or designee at Visits 1 (Day 1), 2 (Day 2), and 7 (Day 22). The ECG will be performed after the patient has rested for at least 3 minutes.

The investigator or subinvestigator will assess whether the ECG is normal or abnormal (see Section 7.6.5.6). If the ECG is deemed abnormal and clinically significant, the investigator or subinvestigator will contact the CRO as per the medical monitoring plan, and it will be recorded as an AE in the eCRF. Results of the ECG and its interpretation also will be entered in the eCRF.

7.6.4 Clinical Laboratory Tests

7.6.4.1 Laboratory Parameters

Blood and urine samples for clinical laboratory tests will be collected Visits 1 (Day 1), 4 (Day 5), 6 (Day 15), and 7 (Day 22), and the date of specimen collection will be entered in the eCRF. Patients will remain in a sitting or supine position during blood collection. The blood sample volumes for clinical laboratory, serum influenza antibody titer, and immunological tests are shown in Table 7-4 below.

Parameter	Total Blood Sample Volume (Per Time Point)
Hematology tests	2 mL
Blood chemistry tests	
Hepatitis B virus surface antigen	25 5
Hepatitis C virus antibody	3.5 - 5 mL
HIV antigen/antibody	
Serum influenza virus antibody titer	3.5 mL

Table 7-4Blood Sample Volumes

7.6.4.2 Routine Laboratory Tests

Routine hematology, blood chemistry, and urinalysis parameters (Table 7-5) will be measured by the clinical laboratory (see Section 7.6.4.5).

Category	Evaluation Items
Hematology tests	Hematocrit (Hct), hemoglobin (Hgb), platelet count, erythrocyte count, and leukocyte (white blood cell [WBC]) count with differential (eosinophil count, basophil count, neutrophil count, monocyte count, lymphocyte count)
Blood chemistry tests	Alanine aminotransferase (ALT), aspartate aminotransferase (AST), total bilirubin (TBL), direct bilirubin, indirect bilirubin, alkaline phosphatase (ALP), gamma glutamyl transferase (GGT), lactate dehydrogenase (LDH), blood urea nitrogen (BUN), creatinine, uric acid, calcium (Ca), chloride (Cl), potassium (K), sodium (Na), total protein, albumin, and C-reactive protein (CRP)
Urinalysis (Qualitative)	Glucose, occult blood, protein, and urobilinogen

Table 7-5 Routine Laboratory Tests

The investigator or subinvestigator will assess whether any abnormal changes from baseline (predose at Visit 1, Day 1) are clinically significant (see Section 7.6.5.6).

7.6.4.3 Immunological Tests

Patients with liver disease, including known chronic hepatitis B and untreated hepatitis C are excluded from enrollment in this study. Patients with untreated HIV infection are also excluded.

The following antigen/antibody tests will be performed for baseline demographic information and to inform clinical management if previously undiagnosed conditions are reported: hepatitis B virus surface (HBs) antigen, hepatitis C virus (HCV) antibody, and HIV antigen/antibody will be measured predose at Visit 1 by the clinical laboratory (see Section 7.6.4.5).

7.6.4.4 Pregnancy Tests

Except for postmenopausal women (defined as cessation of regular menstrual periods for 2 years or more and confirmed by a follicle-stimulating hormone test) and those who are surgically sterile by hysterectomy, bilateral oophorectomy, or tubal ligation, all female patients will undergo a urine pregnancy test predose at Visit 1 (Day 1), Visit 4 (Day 5), and Visit 7 (Day 22) or ET.

7.6.4.5 Sample Collection, Storage, and Shipping

Blood and urine samples and nasopharyngeal/pharyngeal swabs (nasopharyngeal swabs are the preferred method of virology collection as they are the most accurate, but pharyngeal swabs will be acceptable if nasopharyngeal swabs cannot be performed) will be collected by the investigator or designee and sent to the clinical laboratory for processing. Sample collection, handling, labeling, storage, shipping, etc, will be performed according to procedures specified in a separate document.

The sponsor may use any residual blood and/or swab samples collected from patients for the purposes of this study or for future scientific research. When the sponsor decides to perform the test/research, a detailed plan and procedures will be defined. Other than further virology testing, any future use of samples will follow appropriate consent from patients following review by an independent ethics committee. The results of the test/research will be reported in documents separate from the clinical study report for this study.

